7.1 Primary Outcomes

The following primary endpoints will be collected and evaluated in all enrolled patients:

- Device-related Serious Adverse Events – vascular complications including dissection, pseudoaneurysm, hematoma, arteriovenous fistula, thrombus formation, embolization and any vascular complication that may be attributed to the device AND requires surgical repair, surgical wound revision, transfusion, etc.
- Other Serious Adverse Events – permanent cranial nerve injury, new symptomatic ipsilateral hemorrhage and dissections related to ancillary devices
- Functional independence at 90 days (proportion with mRS score 0-2)

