Injury to cranial nerves in the vicinity of the treated carotid artery that has not resolved by three months after the intervention. Symptoms will depend on the specific nerve that is injured, such as hoarseness.

Pre-stroke disability

Obtained at baseline, but representative of the patient's status before the index stroke, assessed by mRS on medical history obtained from patient's medical chart, or family members.

Procedure Related Adverse Event

An undesirable event that occurred as a direct cause of the procedure that was not a direct cause of the study device.

Serious Adverse Event (SAE)

An adverse event in a research patient that led to a death, or led to a serious deterioration in the health of the patient that resulted in a life-threatening illness or injury, or resulted in a permanent impairment of a body structure or a body function, or required in-patient hospitalization or prolongation of existing hospitalization, or resulted in medical or surgical intervention to prevent permanent impairment to body structure or a body function. SAEs are a subset of AEs.

Stroke

A neurological deficit lasting 24 hours or more attributed to an acute focal injury of the central nervous system (CNS) by a vascular cause, including cerebral infarction, intracerebral hemorrhage (ICH), and subarachnoid hemorrhage (SAH). Stroke can be subclassified as Hemorrhagic or Ischemic

Symptomatic Intracranial Hemorrhage (SICH)

New intracranial hemorrhage detected by brain imaging associated with any of the items below (Von Kummer et al. 2015):

- ≥ 4 points total NIHSS at the time of diagnosis compared to the pre-procedure NIHSS.
- ≥ 2 point in one NIHSS category. The rationale for this is to capture new hemorrhages that produce new neurological symptoms, making them clearly symptomatic, but not causing worsening in the original stroke territory. For example, a new remote hemorrhage in the contralateral occipital lobe may cause new hemianopia that is clearly symptomatic, but the patient will not have worsening of ≥ 4 points on the NIHSS score.
- Leading to intubation/hemicraniectomy/EVD placement or other major medical/surgical intervention.
- Absence of alternative explanation for deterioration

Technical Success

Successful introduction of endovascular tools through the NOVIS Transcarotid NPS.

Transient Ischemic Attack (TIA)

Temporary focal brain or retinal deficits caused by vascular disease that resolves completely in less than 24 hours.

[figure not shown]

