2. INTRODUCTION

The purpose of this Statistical Analysis Plan (SAP) is to prospectively outline the methods for analyses for patients with acute ischemic stroke in the anterior circulation due to large vessel occlusion (LVO) who underwent endovascular treatment using the transcarotid approach with flow reversal in this initial feasibility (NITE 1) study using the NOVIS Neuroprotection System (NPS).

The NITE 1 study is a prospective, multi-center, single arm feasibility study for the endovascular treatment of patients with acute ischemic anterior circulation strokes due to large vessel embolic occlusions using the transcarotid approach with flow reversal. Patients enrolled into the NITE 1 study will have failed transfemoral therapy and will be followed immediately from post-op to 90 days. The primary study objective is to establish the feasibility and safety of the NOVIS NPS in the targeted study population, and as such, this SAP will focus on confirming whether the initial safety signal exists from the primary endpoint data.

With FDA's IDE approval of the study design and sample size, the primary safety study endpoints will be numerically compared to existing TCAR data from the ENROUTE NPS clinical program (PROOF and ROADSTER). The functional independence at 90 days will be compared to reference data for acute ischemic stroke (AIS) patients treated with mechanical thrombectomy and the natural history of AIS in those patients who have not received or have failed mechanical thrombectomy, as cited in Section 5. The primary study endpoints for the NITE 1 study include:

- Device-related Serious Adverse Events – vascular complications including dissection, pseudoaneurysm, hematoma, arteriovenous fistula, thrombus formation, embolization and any vascular complication that may be attributed to the device AND requires surgical repair, surgical wound revision, transfusion, etc.
- Other Serious Adverse Events – permanent cranial nerve injury (CNI), new symptomatic intracranial hemorrhage (SICH) and dissections related to ancillary devices
- Functional independence at 90 days (proportion with mRS score 0-2)

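### The symptomatic intracranial hemorrhage definition lets an attribution qualifier count as a sufficient criterion. Make it a required condition and name one NIHSS reference.

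*Protocol*

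**What the plan says.** Protocol Appendix 4 gives the only operational definition of SICH in the two documents: "New intracranial hemorrhage detected by brain imaging associated with any of the items below". Four parallel bullets follow:

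- Item 1, with a threshold of at least 4: "points total NIHSS at the time of diagnosis compared to the pre-procedure NIHSS".
- Item 2, with a threshold of at least 2: "2 point in one NIHSS category. The rationale for this is to capture new hemorrhages that produce new neurological symptoms". No reference score is named.
- Item 3: "Leading to intubation/hemicraniectomy/EVD placement or other major medical/surgical intervention".
- Item 4: "Absence of alternative explanation for deterioration". No minimum size of deterioration is given.

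Neither item 1 nor item 2 says in words that the change must be an increase.

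Protocol Section 7.1 names the outcome components as "permanent cranial nerve injury, new symptomatic ipsilateral hemorrhage and dissections related to ancillary devices". SAP Section 2 names them as "permanent cranial nerve injury (CNI), new symptomatic intracranial hemorrhage (SICH) and dissections related to ancillary devices". SAP Section 8.2.1.2 tabulates new SICH without defining it. SAP Section 5 and its Table 1 compare the incidence with the ENROUTE program and with published thrombectomy data.

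**The concern.** Items 1 to 3 each describe evidence that a bleed is clinically important. Item 4 answers a different question: whether the bleed, and not something else, explains the deterioration. Listing it as one more alternative has two effects. It admits a new bleed with a trivial but unexplained worsening. It also means that attribution is never required of a bleed that meets items 1 to 3. The rationale given under item 2, which justifies a lower threshold for bleeds that miss the 4-point rule, suggests that the authors meant size to matter.

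The stake is a component of a primary safety outcome, set beside external rates in a study of 30 to 60 patients. Two adjudicators who read the list differently could classify the same patient differently, and each such patient visibly moves the reported rate.

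**Working it through.** The documents assume no SICH rate and report none, so there is no planned figure to reproduce. Four checks apply.

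**1. Logic of the list.** Take a patient with a new bleed on imaging. Let A, B and C stand for items 1, 2 and 3 being met, and D for no alternative explanation (item 4). There are 2^4 = 16 patterns.

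| Rule | Patterns counted as SICH |
|---|---|
| As written: A or B or C or D | 16 − 1 = 15 |
| D required: (A or B or C) and D | (2^3 − 1) × 1 = 7 |
| Counted as written, not with D required | 15 − 7 = 8 |
| Counted with D required, not as written | 0 |

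The 8 extra patterns are D alone (1) and every non-empty combination of A, B and C with another explanation present (7). These are logical patterns, not patient frequencies.

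**2. The reference score once D is required.** Item 1 compares with the pre-procedure NIHSS. A patient who has improved by k points must then worsen by at least k + 4 to meet it.

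| NIHSS: pre-procedure, last before bleed, at bleed | Change from pre-procedure | Change from last score |
|---|---|---|
| 18, 6, 16 | 16 − 18 = −2 (not met) | 16 − 6 = +10 (met) |
| 10, 3, 8 | 8 − 10 = −2 (not met) | 8 − 3 = +5 (met) |
| 18, 6, 22 | 22 − 18 = +4 (met) | 22 − 6 = +16 (met) |

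In the first patient k = 12, so 16 points of worsening are needed. As written, that patient still counts through item 4 if nothing else explains the change, and perhaps through items 2 or 3. Once D is required, the patient is lost if item 2 is also scored from the pre-procedure value and no major intervention follows. Repairing the logic therefore exposes the reference problem, and the two changes belong together.

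**3. Weight of one patient.** Protocol Section 14.2 plans 30 to 40 per-protocol patients and at most 60 in the ITT population. SAP Section 8 uses all subjects as the denominator.

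- n=30: 1/30 = 3.3 points
- n=40: 1/40 = 2.5 points
- n=60: 1/60 = 1.7 points

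Exact (Clopper-Pearson) 95% intervals: 1 of 30 is 3.3% (0.1 to 17.2), 2 of 30 is 6.7% (0.8 to 22.1), 1 of 60 is 1.7% (0.0 to 8.9) and 2 of 60 is 3.3% (0.4 to 11.5).

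**4. Endpoint wording side by side.** The example under item 2 in Appendix 4 is a remote bleed in the contralateral occipital lobe. That patient has SICH by the definition and counts under the SAP's term. Under the ipsilateral wording of Protocol Section 7.1, the same patient does not count.

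**The case against.** Several points on the other side have force.

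- **Seriousness.** The outcome covers serious adverse events, so a trivial bleed would also have to meet Protocol Section 12.2. If that is applied, it narrows the over-count. It does not remove it: a bleed that prolongs hospitalization is serious whatever the NIHSS change. Nor does it supply the missing attribution test for items 1 to 3.
- **Pre-procedure reference.** Appendix 1 ties the 24-hour NIHSS and CT/CTA to finding symptomatic hemorrhage. For a bleed found by then, the pre-procedure score is the only earlier scheduled one. This stands, and the fix keeps that score as the fallback.
- **Adjudication.** A clinical events committee may read item 4 sensibly. Its charter is not among the documents, so this can be neither relied on nor ruled out.
- **Precision.** No hypothesis is tested (Protocol Section 14.3), and the intervals above are wide whichever rule is used. This lowers the severity but does not make the rule right.

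A reader might also infer stronger claims that the documents do not support:

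- *The definition as written both over-counts and misses bleeds.* These belong to different readings. The rule that over-counts also captures, through item 4, the bleed that item 1 misses (0 of 16 patterns lost).
- *Worsening is measured only from the pre-procedure NIHSS.* Only item 1 names that reference. Item 2 names none, and items 3 and 4 name no NIHSS score.
- *The thresholds are redundant.* Items 1 to 3 still decide every case with an alternative explanation, which is 7 of the 15 qualifying patterns.
- *The external comparison is uninterpretable.* The comparators' definitions are not in the documents, so the damage cannot be measured.
- *The committee applies this exact text.* Protocol Section 13.2 says only that it adjudicates potential endpoint events under its charter.

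**Conclusion.** The definition is wrong as written, at moderate severity. Item 4 is sufficient where it should be necessary, no other section corrects it, and the SAP adds no definition of its own. Relative to the repaired rule, the literal reading can only add cases, because every repaired case satisfies item 4. How many it would add is unknown, since the documents give no expected SICH rate and no frequency of competing explanations. The size is therefore stated per patient: 3.3, 2.5 or 1.7 points at n=30, 40 or 60.

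The conclusion rests on reading the four bullets as a plain list of alternatives, which is what the lead-in says. If adjudicators already treat item 4 as required, the over-count disappears, but the reference gap in items 1 and 2 becomes live. The wording needs settling on either reading.

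**What to change.** Replace the SICH entry in Protocol Appendix 4 with a rule of this form: a new intracranial hemorrhage on brain imaging, with at least one of items 1 to 3, **and** no alternative explanation for the deterioration. State that items 1 and 2 mean an increase in NIHSS from one named reference: the most recent NIHSS before the deterioration, or the pre-procedure score if there is no later one.

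Use the same text in the SAP and the clinical events committee charter. Reconcile the ipsilateral wording in Protocol Sections 1 and 7.1 with the SAP's SICH, so that a contralateral bleed is classified the same way in both documents.

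The cost is wording in the Protocol, SAP and charter, plus a re-read of any bleed already adjudicated. No new data are needed. NIHSS is already required before the procedure, at 24 hours, at day 5 to 7 or discharge, and at 90 days (with the phone-visit exception), and is to be repeated for a suspected neurological event (Protocol Sections 10.2 and 11).

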1. LIST OF ABBREVIATIONS

Abbreviations and Terms	Explanation
ACT	Activated Clotting Time
AIS	Acute Ischemic Stroke
CEA	Carotid Endarterectomy
CNI	Cranial Nerve Injury
DAPT	Dual Antiplatelet Therapy
ITT	Intention to Treat
LVO	Large Vessel Occlusion
MAE	Major Adverse Event
MI	Myocardial infarction
NPS	Neuroprotection System
PP	Per Protocol
SAE	Serious Adverse Events
SAP	Statistical Analysis Plan
SICH	Symptomatic Intracranial Hemorrhage
TCAR	Transcarotid Artery Revascularization

2. INTRODUCTION

The purpose of this Statistical Analysis Plan (SAP) is to prospectively outline the methods for analyses for patients with acute ischemic stroke in the anterior circulation due to large vessel occlusion (LVO) who underwent endovascular treatment using the transcarotid approach with flow reversal in this initial feasibility (NITE 1) study using the NOVIS Neuroprotection System (NPS).

The NITE 1 study is a prospective, multi-center, single arm feasibility study for the endovascular treatment of patients with acute ischemic anterior circulation strokes due to large vessel embolic occlusions using the transcarotid approach with flow reversal. Patients enrolled into the NITE 1 study will have failed transfemoral therapy and will be followed immediately from post-op to 90 days. The primary study objective is to establish the feasibility and safety of the NOVIS NPS in the targeted study population, and as such, this SAP will focus on confirming whether the initial safety signal exists from the primary endpoint data.

With FDA's IDE approval of the study design and sample size, the primary safety study endpoints will be numerically compared to existing TCAR data from the ENROUTE NPS clinical program (PROOF and ROADSTER). The functional independence at 90 days will be compared to reference data for acute ischemic stroke (AIS) patients treated with mechanical thrombectomy and the natural history of AIS in those patients who have not received or have failed mechanical thrombectomy, as cited in Section 5. The primary study endpoints for the NITE 1 study include:

- Device-related Serious Adverse Events – vascular complications including dissection, pseudoaneurysm, hematoma, arteriovenous fistula, thrombus formation, embolization and any vascular complication that may be attributed to the device AND requires surgical repair, surgical wound revision, transfusion, etc.
- Other Serious Adverse Events – permanent cranial nerve injury (CNI), new symptomatic intracranial hemorrhage (SICH) and dissections related to ancillary devices
- Functional independence at 90 days (proportion with mRS score 0-2)

Serious Adverse Events will be tabulated and reported accordingly. The primary endpoint and all secondary endpoints will be analyzed based on both the ITT and PP population. All available data on the ITT patients who were enrolled in the study will be included. This SAP presents the data results to be reviewed in evaluating the device-related SAEs, other SAEs, and functional independence at 90 days. Secondary endpoints to be summarized include the following:

- Carotid access time
 - Hospital arrival to neck incision
 - Neck incision to carotid exposure
 - Neck incision to carotid artery catheterization (includes securement of sheath)
 - Neck incision to femoral venous sheath access (includes securement of sheath)
 - Neck incision to initiation of reverse flow
- Time to final revascularization
 - Hospital arrival to OR
 - Last known well to final revascularization

- Admission to final revascularization
- OR to final revascularization
- Cutdown to final revascularization
- Arterial introduction of interventional tools to final revascularization
- Total reverse flow time (CCA clamp to CCA unclamp)
- Device-related complications
- Neurologic assessment at 90 days (proportion of patients with a nondisabling or disabling stroke according to NIHSS)
- Technical success rate – Successful introduction of endovascular tools through the NOVIS Transcarotid NPS.
- Rates of revascularization success assessed by angiographic core lab (mTICI \geq 2b)

To determine if the NOVIS NPS patients are comparable in safety to TCAR patients using the ENROUTE NPS, the following mutually exclusive populations will be compared:

Within the ***Complete NOVIS NPS Population***: All NOVIS NPS patients who were enrolled as part of the ITT study population in the NITE 1 study.

Within the ***Complete TCAR Population***: All TCAR patients who were enrolled in the ENROUTE clinical program (PROOF, and ROADSTER studies) and underwent the procedure.

There will be two independent sets of analyses performed to assess comparability between both patient populations – one using the ITT NITE 1 study population and the second using the Per Protocol NITE study population. The research questions, datasets, methods of analysis, and summarization of the results will be discussed in this SAP. The general design of the analysis summary tables, figures, and patient data listings used to present the analysis results are also presented in this plan.

The planned analyses identified in this SAP may be included in regulatory submissions, medical presentations and manuscripts. Exploratory analyses, not pre-identified in this SAP, may be performed to support the clinical development program.

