14.2 Sample Size

A minimum of 30 and a maximum of 40 patients will be enrolled into the PP population and analyzed in this study. Enrollment in the ITT cohort will cease when 30 PP patients have been accrued. Additional patients beyond 30 who are successfully enrolled while waiting for the 30th PP patient to complete the 90-day follow-up period, will be analyzed in the cohort for which they qualify, whether PP or ITT. Enrollment will continue till a maximum of 60 patients are enrolled in the ITT population or the DSMB stops the study for safety reasons.

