As listed above, the first data review will compare the incidence of the device-related SAEs from NITE 1 to the device-related SAEs collected across the body of TCAR evidence to date. This comparison group will include device-related SAEs from the ENROUTE NPS clinical program (e.g., PROOF and ROADSTER) representing a patient population spanning from feasibility to pivotal to post-market study settings. In addition, the incidence of permanent CNI and new SICH from the NITE 1 patient population will be compared to the same comparison group as well as reference data for AIS patients treated with mechanical thrombectomy and the natural history of AIS in those patients who have not received or have failed mechanical thrombectomy. The use of ENROUTE NPS clinical program data as a point of comparison for device-related SAEs and permanent CNI is based on the comparability of ENROUTE NPS and NOVIS NPS. Although each device is used for different patient populations, the surgical approach and set-up of each NPS device are equivalent. In regard to new symptomatic hemorrhage, the risk for this event can be attributed to two main causes: the risk due to cerebral reperfusion injury and the risk due to interventional or mechanical manipulation of the cerebral vasculature. The first applies to both ENROUTE NPS and NOVIS NPS, since any carotid revascularization comes with risk for cerebral reperfusion injury. The latter may be considered more specific to the AIS patient population. However, due to the increased risk for bleeding among patients treated with ENROUTE NPS due to required use of DAPT pre-procedure and systemic heparinization during the procedure to achieve an ACT of > 250, which is not applicable in the NOVIS NPS procedure for AIS patients, these risks can be considered to offset one another in each population. Therefore, the occurrence for SICH from ENROUTE NPS procedures can be compared to NOVIS NPS. Next, the incidence of dissections related to ancillary devices will be compared to the dissections related to the ancillary devices used commercially for ENROUTE and captured through post-market surveillance data. These numerical comparisons are summarized below with reference to the outcome, comparison group. Finally, the functional modified Rankin Score (mRS) at 90 days will be compared to the average functional independence score at 90 days (mRS 0-2) from the relevant studies included in the meta-analysis by Mokin M, et al in AIS patients treated with mechanical thrombectomy and the natural history of AIS in those patients who have not received or have failed mechanical thrombectomy. These data comparisons are summarized in Table 1 below:

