8. SAFETY

Safety will be assessed by the Data Safety Monitoring Board and events will be adjudicated for review by the Clinical Events Committee, as outlined in the NITE 1 protocol. For final analysis of the safety events, binary rates will be calculated using a denominator as the number of all subjects in the study regardless of their follow-up time.

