8.2.1.1. Summary of Device-Related Serious Adverse Events

All summaries of device-related SAEs will be presented separately and for the individual events.

The number and percentage of patients experiencing device-related SAEs will be summarized. Summary Table 6.6.1 entitled *Summary of Site-Reported Device-Related Serious Adverse Events* will include counts and percentages of patients (and event counts) following the category listed below. Results will be supported by the data presented in Listing 6.6 *Serious Adverse Events*, sorted by patient number and the date of procedure.

- vascular complications including dissection
- pseudoaneurysm
- hematoma
- arteriovenous fistula
- thrombus formation
- embolization
- any vascular complication that may be attributed to the device AND requires surgical repair, surgical wound revision, or transfusion

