8.2.1.2. Summaries of Other SAEs

All summaries of other SAEs will be presented separately and for the individual events:

- Permanent CNI
- New SICH
- Dissections related to ancillary devices

The number and percentage of patients experiencing other SAEs will be summarized. Summary Table 6.6.2 entitled *Summary of Other Serious Adverse Events* will include counts and percentages of patients (and event counts) following the category listed above.

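### The SAP asks whether NOVIS is comparable in safety to ENROUTE TCAR but plans only bare rates without intervals; at this sample size these cannot support comparability and can reveal only a large excess.

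*SAP*

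**What the plan says.** SAP Section 2 (Introduction) gives the purpose of the between-population comparison: "To determine if the NOVIS NPS patients are comparable in safety to TCAR patients using the ENROUTE NPS". Two sets of analyses follow, one on the ITT population and one on the per-protocol population.

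The method is numerical throughout. Section 2 says that "the primary safety study endpoints will be numerically compared to existing TCAR data". Section 5 adds: "These numerical comparisons are summarized below with reference to the outcome, comparison group". Table 1 in that section lists an outcome and a comparison group for each row and nothing more. Section 8 fixes the denominator: "binary rates will be calculated using a denominator as the number of all subjects in the study regardless of their follow-up time". For the other SAEs, Section 8.2.1.2 says that the table "will include counts and percentages of patients (and event counts) following the category listed above", and Section 8.2.1.1 uses the same format for device-related SAEs.

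On size, Protocol Section 14.2 says: "A minimum of 30 and a maximum of 40 patients will be enrolled into the PP population and analyzed in this study". It also says: "Enrollment will continue till a maximum of 60 patients are enrolled in the ITT population". Protocol Section 14.3 states that no formal hypothesis is tested, because this is a small feasibility study.

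**The concern.** The question and the planned output do not match. Judging whether two populations are comparable requires knowing how far apart the true rates could be, given the data. A count and a percentage placed beside another percentage do not show that. No interval is planned for the NITE 1 rate, the benchmark or the difference, and no margin or threshold is given.

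The benchmark events are uncommon, around 2% in ROADSTER, and NITE 1 is small. A display of 0% against 1.8% could reassure a reader when the true risk is several times higher. One event in 30 could alarm a reader when the risk is unchanged. SAP Section 2 says that the planned analyses may go into regulatory submissions, presentations and manuscripts, so such a display may be read without its context.

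**Working it through.** **Inputs from the documents**
- Per-protocol size 30 to 40; ITT maximum 60 (Protocol 14.2).
- ROADSTER serious dissection 4/219 = 1.8% (Protocol 3.2.2). The stated percentage reproduces: 4/219 = 0.0183.

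**Assumptions**
- The SAP's comparator pools PROOF and ROADSTER. That pooled device-related SAE rate is not in the documents, so the ROADSTER dissection rate stands in for it as an illustration.
- The 95% level and the two-sided 0.05 level are chosen here; the documents state neither. The sample size comes with no precision or power target, so there is no derivation to reproduce.

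**Step 1. What zero events would mean.** The exact two-sided 95% upper limit for 0/n is 1 − 0.025^(1/n).
- n=30: 11.6%
- n=40: 8.8%
- n=60: 6.0%

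The exact (Clopper-Pearson) interval for 4/219 is 0.5% to 4.6%. Even the best possible NITE 1 result leaves an upper limit above that range. One event in 30 (3.3%) has an interval of 0.1% to 17.2%.

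**Step 2. Chance of false reassurance.** Suppose that the true rate is tripled, 3 × 1.8% = 5.4%. The probability of no events is (1 − 0.054)^n.
- n=30: 18.9%
- n=40: 10.9%
- n=60: 3.6%

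**Step 3. Chance of a false alarm.** Suppose that the true rate is unchanged at 1.8%. At n=30 and n=40, one event (3.3% and 2.5%) already looks worse, so the probability is 1 − (1 − 0.018)^n. At n=60, one event is 1.7%, which is not worse than 1.8%, so two are needed.
- n=30, at least one event: 42%
- n=40, at least one event: 52%
- n=60, at least two events: 29%

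**Step 4. What could be separated from ROADSTER.** Fisher's exact test, two-sided, against 4/219:

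| NITE 1 result | p |
|---|---|
| 1/30 | 0.48 |
| 2/30 | 0.16 |
| 3/30 | 0.040 |
| 3/40 | 0.077 |
| 4/40 | 0.022 |
| 4/60 | 0.068 |
| 5/60 | 0.024 |

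The thresholds are therefore 3 of 30, 4 of 40 and 5 of 60. At a true rate of 5.4%, binomial tails give the chance of reaching them as 22%, 17% and 22%. At a true rate of 15% the chances are 85%, 87% and 96%. A large excess would usually show; a tripling usually would not.

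**The case against.** The strongest reply is that the plan is openly descriptive. Protocol 14.3 disclaims hypothesis testing, and SAP Section 2 calls the comparison numerical, speaks of an initial safety signal and refers to FDA's IDE approval of the design and sample size. Safety action during the trial belongs to the DSMB under its charter. All of this stands, and it means that the absence of a test is not a defect. It does not supply an interval, and it sits awkwardly beside an aim of settling whether the two populations are comparable. An interval is itself descriptive.

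A reader might infer more than the documents support:
- That the SAP presumes comparability, or will label a chance result comparable or a signal. It poses comparability as a question and contains no rule that labels any result. The risk is that readers over-interpret point estimates.
- That the sample can show nothing in either direction. Step 4 shows that a large excess is detectable.
- That 30 to 40 is the whole range. It is the per-protocol range; the ITT set, named first for the comparison, may reach 60. The limits narrow, but the conclusion is the same.
- That every external comparison should be a risk difference with an interval. For 90-day mRS and part of the symptomatic hemorrhage comparison, the reference is published literature. For ancillary-device dissections, the Section 5 text points to post-market surveillance with no denominator given. A difference is workable only where ENROUTE patient counts exist.

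Section 5 also concedes that the two devices serve different patient populations. An interval measures sampling error only and does not make them alike.

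**Conclusion.** The point holds as a mismatch between a stated aim and its planned output. Bare rates from 30 to 60 patients cannot support a statement of comparable safety against benchmarks near 2%, and they can reveal only a large excess. With no events observed, true rates of up to 6.0% to 11.6% remain compatible with the data, depending on n. The chances of misleading reassurance or alarm rest on one ROADSTER component used as a stand-in, on treating 1.8% as the true reference rate, and on a tripling as the example. A different pooled rate would change those percentages. The upper limits for zero events do not depend on the benchmark.

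This should be corrected before the analysis. It calls for no change to the design, the enrolment or the decision not to test a hypothesis.

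**What to change.** In SAP Sections 2, 5, 8 and 9:
1. Report each NITE 1 primary endpoint proportion, in both the ITT and per-protocol sets, with an exact (Clopper-Pearson) 95% confidence interval.
2. Beside it, show the comparator's count, denominator and exact interval wherever counts exist. Add a risk difference with its interval only for comparisons with ENROUTE patient counts.
3. Reword the Section 2 aim so that the analysis describes, with 95% intervals, how NITE 1 rates relate to ENROUTE rates.
4. State that comparability is not concluded from point estimates, and that the intervals reflect sampling error only, not differences between the populations.

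The cost is a few lines of text and minor programming. The safety statement may look less favourable once the upper limits are visible.
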